- ^{18F}Florbetapir PET SUVR: Mean standardized uptake value ratio (SUVR) from the medial orbitofrontal cortex, anterior cingulate, parietal lobe, posterior cingulate, temporal lobe, and precuneus, normalized to cerebellar gray matter.
- ^{18F}MK-6240 PET SUVR (Medial Temporal): SUVR averaged across medial temporal regions including the amygdala, hippocampus, entorhinal cortex, and parahippocampus.
- ^{18F}MK-6240 PET SUVR (Global Mean): SUVR global mean normalized to cerebellar gray matter.
- MRI Cortical Thickness: Mean cortical thickness across nine predefined brain regions.
- MRI Hippocampal Volume: Volume of the hippocampus.

All imaging measures were collected at baseline and 78 weeks. The outcomes are defined as the change in each measure from baseline to 78 weeks.

4. Sample Size Calculation.

The sample size calculation was based on the primary outcome: change in ADAS-Cog11 scores from baseline to 78 weeks, using the RMASS program for longitudinal studies. Assuming a within-subject correlation of r=0.3 (moderate correlation) for repeated measures and a uniform dropout rate reaching 15% by 78 weeks, a total sample size of 130 participants (65 per arm) was originally projected to detect Cohen's d of 0.50 with 80% power at 5% significance level. With approval from sponsor (NIA) and DSMB, the recruitment target was reduced to 120 participants due to pandemic-related recruitment delays and required study completion within the extended funding timeline. For n=120, the minimum detectable effect size increased slightly to a Cohen's d of 0.52.

5. Statistical analysis

The analyses were conducted on the Intent-to-treat (ITT) sample, i.e., all randomized participants according to the treatment that they were assigned. All hypotheses were tested at level of significance of 5%. There was no adjustment for multiple statistical comparisons in this trial. All analyses were conducted using R.

We first examined patients' baseline characteristics to ensure that covariates were balanced between treatment and placebo arms. Continuous variables were summarized using means and standard deviations, while categorical variables were summarized using counts and percentages.

Linear mixed effects models were used to evaluate the efficacy of Valacyclovir as compared to placebo on cognitive and functional outcomes. Specifically, for each outcome measure, we considered the following model

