$$\Delta Y_{it} = \beta_0 + \beta_1 * Group_i + \alpha * Time_{it} + \gamma * Group_i * Time_{it} + \delta Y_{i0} + b_i + \epsilon_{it}, \tag{1}$$

where ΔY_{it} is change of the outcome measure (week t minus baseline) for subject i at timepoint t, $Group_i$ is the treatment group indicator for subject i (1= Valacyclovir and 0=placebo), $Time_{it}$ is the visit time point (treated as a categorical variable), Y_{i0} is baseline value of the outcome measure for subject i, b_i is a subject-specific random intercept, and ϵ_{it} is the unexplained

residual error term. $(\beta_0, \beta_1, \alpha, \gamma, \delta)$ are fixed effects parameters. The efficacy of Valacyclovir versus placebo at each time point was tested by forming contrasts of the fitted model. The model was further adjusted for key demographic and genetic variables, including age, sex, and apolipoprotein E $\varepsilon 4$ carrier status. Missing data on outcome variables were dealt with by using (longitudinal) linear mixed effects models which do not require complete measurements under the "missing at random" assumption.

For the primary outcome (ADAS-Cog 11), a series of sensitivity analyses were conducted to evaluate the robustness of the findings across key clinical subgroups and under different analytic assumptions. These included: 1) a per-protocol analysis limited to participants who completed the study; 2) a subgroup analysis of participants who received cholinesterase inhibitors or memantine; and 3) a subgroup analysis of participants with a baseline 18F-Florbetapir PET $SUVR \ge 1.15$ (amyloid positive for AD).

Linear regression analyses were performed to evaluate the effect of Valacyclovir on changes in imaging outcomes from baseline to 78 weeks. Each model included the baseline value of the corresponding imaging measure as a covariate to control for initial differences. The models were further adjusted for key demographic and genetic variables, including age, sex, and apolipoprotein E & carrier status. To assess the robustness of the findings and address potential bias due to missing data at follow-up, sensitivity analyses were conducted using weighted linear regression. In these models, the weights were calculated as the inverse probability of a subject being a completer, with probabilities estimated using logistic regression with ridge regularization to handle potential collinearity among baseline variables.

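### Model (1) gives baseline ADAS-Cog11 one coefficient for all visits, so a chance baseline imbalance may be only partly removed at week 78; the SAP also does not say which fit carries the primary test.

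*SAP*

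**What the plan says.** SAP section 3 makes ADAS-Cog11 the primary outcome and change from baseline to week 78 the primary endpoint. Section 5 writes out model (1) for change from baseline. It has group, categorical visit, group by visit, one coefficient δ on the baseline value, and a subject-specific random intercept. The model has no baseline-by-visit term.

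On testing, the SAP says: "The efficacy of Valacyclovir versus placebo at each time point was tested by forming contrasts of the fitted model". The next sentence adds: "The model was further adjusted for key demographic and genetic variables, including age, sex, and apolipoprotein E" ε4 carrier status. These three covariates appear neither in the equation nor in its list of fixed effects, and the list is introduced as open-ended. The form of the added terms (main effects, or by visit) is not given. The adjusted fit is not among the three sensitivity analyses listed for ADAS-Cog11.

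On the error rate, the SAP says "All hypotheses were tested at level of significance of 5" per cent, and "There was no adjustment for multiple statistical comparisons in this trial".

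The statistical section inside the Protocol repeats this text. The Protocol's section on intent to treat, dropouts and missing data names no covariates. Its Specific Aims mention age, sex and APOE ε4 only as potential moderators in exploratory analyses.

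**The concern.** There are two separate issues.

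The first is the single δ. In a progressive disease, a prognostic baseline score may predict an 18-month change more strongly than a 12-week change. One shared coefficient is then a compromise across visits: too large at week 12 and too small at week 78. If the arms differ by chance at baseline, the week-78 contrast is only partly corrected, and some of the precision that baseline adjustment should give is lost. Treatment is allowed to vary by visit, so a constant baseline effect is a restriction with no stated reason.

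The second is the identity of the primary test. A reader cannot tell whether the week-78 contrast that decides the trial comes from model (1) as printed or from the version with age, sex and APOE ε4. If both exist and no rule chooses between them, two p-values compete for one 5% test.

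**Working it through.** **The plan's own figure.** The SAP says that 130 participants were "originally projected to detect Cohen's d of 0.50 with 80% power at 5% significance level". Its inputs are: "Assuming a within-subject correlation of r=0.3 (moderate correlation) for repeated measures", and a "uniform dropout rate reaching 15% by 78 weeks". The exact program settings are not given. I assumed a two-sided normal approximation with baseline adjustment and 85% retained:

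- Per arm 65 × 0.85 = 55.25; SD factor √(1 − 0.3²) = 0.954.
- SE = 0.954 × √(2/55.25) = 0.1815; 0.50/0.1815 = 2.755; power = Φ(2.755 − 1.960) = 78.7%.
- A repeated-measures version with five visits and linear attrition gives 79.1% for 130, and 79.0% for 120 at d = 0.52.
- 0.50 × √(130/120) = 0.520, which agrees with "For n=120, the minimum detectable effect size increased slightly to a Cohen's d of 0.52".

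The sample size statement is reproduced to within about 2 points and is not in dispute here.

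**Error left by a single baseline coefficient.** These inputs are assumptions, because the documents give no ADAS-Cog variances: baseline SD 7, SD of the subject's 78-week change slope 7, baseline-slope correlation ρ = 0.3 to 0.5, linear decline. The visits (12, 26, 52, 78) are from the SAP.

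- True baseline coefficient at week t: ρ × (7/7) × t/78.
- With complete data and a random intercept, the single δ estimates the average over visits. Mean visit time = (12 + 26 + 52 + 78)/4 = 42 weeks, so δ is about ρ × 42/78.
- Shortfall at week 78: ρ × (1 − 42/78) = 0.4615ρ.
- ρ = 0.3 gives 0.14; ρ = 0.5 gives 0.23 points per point of imbalance.
- Typical imbalance (one SE, 60 per arm): 7 × √(2/60) = 1.28 points.
- Left in the week-78 estimate: 0.14 × 1.28 = 0.18 to 0.23 × 1.28 = 0.29 points.

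Simulations with 15% dropout agree. They leave between 0.14 and 0.23 per point with the single coefficient, and about 0.00 to 0.02 with baseline by visit. The interaction lowers the week-78 variance by 1 to 5%. If baseline is unrelated to slope (ρ = 0), it raises it by about 1%.

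For scale, if the SD of the week-78 change is at least 7, then d = 0.52 is at least 0.52 × 7 = 3.64 points. The residual is then at most about 0.18/3.64 = 5% to 0.29/3.64 = 8% of that effect.

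**Average bias.** In a 4,000-run REML simulation (n = 120, non-differential dropout), week-78 bias was about 0.003 SD or less for model (1). Bias of about 0.055 SD appeared only when dropout was made to depend on baseline in opposite directions in the two arms. Covariate-by-visit terms removed it.

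**Two fits, if either may be claimed.** Suppose age, sex and APOE ε4 explain a share R² of the outcome variance (assumed). Under the null, the two test statistics are then approximately bivariate normal with correlation √(1 − R²).

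| R² | Correlation | P(either p < 0.05) |
|---|---|---|
| 5% | 0.975 | 6.0% |
| 10% | 0.949 | 6.5% |
| 20% | 0.894 | 7.1% |

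A separate null simulation gave 6.2%, 6.6% and 7.0%, with each fit alone at 4.9 to 5.1%.

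**What baseline by visit does not fix.** With an assumed subject slope SD of 7, the random-intercept model rejected about 16 to 19% under the null, with or without baseline-by-visit terms. In a second setting with growing residual variance, a model with all covariate-by-visit terms still rejected 12.6%.

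**The case against.** The strongest reply is that the adjustment sentence describes one final model with three added covariates, not a second analysis. The singular wording, its absence from the sensitivity list and the parallel wording for the imaging models all fit that reading. The SAP also fixes the outcome and the week. This stands: two competing tests is one reading, not a fact. Even so, the final model would then not be the one printed, and its covariate list and terms would still be open.

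Three stronger inferences are tempting, and the documents do not support them:

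- That the 5% level is breached by two versions. Nothing in the SAP says either fit may be claimed, and each alone holds its level in the simple setting. The excess needs two fits, a free choice between them and an assumed R².
- That week 78 is biased. Randomisation protects the contrast on average. The point concerns what remains of a chance imbalance in this one trial, and some precision.
- That age, sex and APOE ε4 are also held constant across visits. Only the baseline term is written out.

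It can also be said that the effect is small and rests on an assumed baseline-slope correlation. That is fair, and it limits the weight of the point. The counterweight is that the change costs very little.

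**Conclusion.** The point holds in a limited form. The constant baseline coefficient is printed in the equation, and a visit-specific one suits a week-78 endpoint better. For ρ = 0.3 to 0.5 and SDs of 7, about 0.2 to 0.3 ADAS-Cog points of a typical chance imbalance are left in the primary estimate, and its variance is 1 to 5% higher than it need be. At ρ = 0 there is nothing to gain.

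The missing statement of which fit is primary is a gap in specification, not a demonstrated error. The 6 to 7% rate is conditional on both fits being run and either being claimable.

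A reader might infer that baseline-by-visit terms would secure the 5% level. They would not. If variance grows over visits, the random-intercept covariance is the larger threat, and it needs its own correction.

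**What to change.** In SAP section 5, and in the matching Protocol text:

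1. Add a baseline-by-visit term to model (1).
2. Name one model whose week-78 contrast is the primary test, for example the model with age, sex and APOE ε4 as a closed list, with every term written out.
3. Label the other version supportive.
4. The SAP is dated July 14, 2025 and written in the past tense. Unless an earlier dated plan shows the choice, state that it was made after the fact; naming a model now cannot restore prespecification.

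Visit interactions for age, sex and APOE ε4 are optional.

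The cost is wording and one model change. One baseline coefficient becomes four, so there are three extra parameters, with about 120 × 0.85 = 102 participants expected at week 78 under the plan's dropout assumption. If baseline is unrelated to decline, the variance rises by about 1%. The covariance structure should be dealt with separately, for example by an unstructured or visit-specific covariance.

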Anti-viral Therapy in Alzheimer's Disease

NCT03282916

July 14, 2025

Introduction

This multicenter project is funded by grant number R01AG055422 from the National Institute on Aging, P.I. [name] [name]. The recipient organization is Columbia University (CU). Since many procedures are conducted at New York State Psychiatric Institute (NYSPI) through a Research Foundation for Mental Hygiene (RFMH) subcontract, the term "NYSPI" is used to refer to CU/NYSPI conduct of the protocol. By default, all policies and procedures refer to CU/NYSPI, and procedures specific to the two other sites, New York University (NYU; PI [name]) and Banner Alzheimer's Institute (BAI; PI [name]), are indicated accordingly.

In this study, we will be conducting the first controlled clinical trial to directly address the long-standing viral etiology hypothesis of Alzheimer's disease (AD) which posits that viruses, particularly the very common herpes simplex virus-1 (HSV1) and herpes simplex virus-2 (HSV2), may be etiologic or contribute to the pathology of AD.

The generic antiviral drug valacyclovir at 4 g per day, repurposed as an anti-AD drug, will be compared to matching placebo in the treatment of 130 patients (65 valacyclovir, 65 placebo) with mild AD in a randomized, double-blind, 18-month Phase II proof of concept trial. Participants are required to be seropositive for HSV1 or HSV2. The targeted number of participants was reduced from 130 to 120 (60 valacyclovir, 60 placebo) because of delays due to the COVID pandemic and the funding timeline. This change was approved by the DSMB and the sponsor, NIA.

We hypothesize that patients treated with valacyclovir will show less decline in cognition and function compared to placebo; will show less amyloid accumulation than those on placebo using 18F-Florbetapir PET imaging, and less tau binding than those on placebo using 18F-MK-6240 tau PET Imaging.

Background

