Valacyclovir is the most widely used generic antiviral drug with over 20 years of worldwide use. It is approved for the treatment of HSV1, HSV2, varicella zoster (shingles), and chickenpox. No other available antiviral drug, e.g., acyclovir (intravenous), famciclovir and ganciclovir, has been shown to be superior to valacyclovir in the treatment of HSV1 and HSV2. Recommended dose of oral valacyclovir for peripheral acute HSV infections is 1 to 3 g daily, and bioavailability is 54%. For long-term HSV suppression, the dose is 1 g daily. In patients with HIV infection and clinical AIDS, valacyclovir 8 g/day was associated with serious adverse events in 10% of patients including GI disturbances and headache, and thrombotic microangiopathy in a few cases. Doses of 6-8 g daily are tolerated in healthy young adults. The difficulty in obtaining efficacy for any drug in AD has led us to target a dose of valacyclovir 4 g daily in this proof-of-concept trial; 3 g is approved for peripheral HSV infection and was effective in the schizophrenia pilot trial.

Based on our experience to date in the conduct of this protocol, which is consistent with U.S. prevalence rates, HSV1/HSV2 seropositivity rate is estimated to be 60-65%.

Participants can continue on cholinesterase inhibitors and/or memantine, if doses are stable for 1 month prior to study entry. Major neurological and psychiatric disorders are excluded. Psychotropic and other medications will be permitted. Medication dosage may be changed if indicated by the study physician. All medication changes will be documented using the National Alzheimer's Coordinating Center (NACC) rating form for possible ancillary analyses. Valacyclovir does not have any major drug-drug/drug-food interactions.

SPECIFIC AIMS.

The aim is to evaluate valacyclovir, a repurposed generic antiviral drug, as a treatment for early AD. An additional aim is to evaluate the effect of valacyclovir on biomarkers of AD. VALAD is a Phase II, proof of concept (POC), randomized, double-blind, placebo-controlled, 18-month treatment trial with early AD and antibodies to HSV1 or HSV2.

Hypothesis 1. Patients treated with valacyclovir will show smaller decline than patients treated with placebo on the ADAS-Cog11 (primary outcome; cognitive measure, 0 to 78 weeks).

Hypothesis 2. Patients treated with valacyclovir will show smaller decline than patients treated with placebo on the ADCS-ADL (secondary outcome; function measure, 0 to 78 weeks).

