Each patient that has an AE or SAE reported will have an AE log filed in their research chart. Both AE and SAE are to be recorded on the AE log. AE logs are data forms for this study. Hardcopy AE forms are rewritten each time new information about the event is made available, with all revisions kept in paper research charts. However, the database AE form will only contain information reflecting the final resolved event or last recorded information once the patient has left the protocol. Information regarding the treatment provided, outcome, and presumed relationship to study drug will be updated as new information becomes available. Site PIs will sign the bottom of the AE logs for their own site once the patient has exited the protocol.

SAEs are also logged on the AE form for data purposes in this study. For any SAE occurring at NYU or BAI, the SAE will first be reported to local IRB, then to NYSPI for local follow up reporting when applicable, as well as for follow up reporting to additional oversight bodies as described above (DSMB, IRB).

All information obtained between visits by the study coordinator that may be an AE or SAE needs to be communicated to the study physician who will then decide if it is an AE or SAE, consulting with [name] if necessary. Based on the decision, the study coordinator needs to ensure that the AE and SAE

forms and completed and submitted to the relevant agencies. Individual AEs need not be reported outside of the core research group and database team. SAEs need to be reported to the IRB and DSMB and NIA.

Protocol Deviations:

If unavoidable deviations from the study protocol occur, they will be recorded on a protocol deviation form filed in the patient's research chart. A protocol deviation log of all deviations throughout the protocol for every patient will be filed in the site's regulatory binder. Site coordinators will keep a log of protocol deviations in an excel document for continual reference and recording.

Protocol Exceptions:

Requests for protocol exceptions are submitted to local IRB on a case by case basis.

Caregiver Communications:

Coordinators will log all clinically relevant communications with patients and their caregivers in the VALAD charts. The only communications that should not be recorded are those initiated by the coordinator, and those regarding scheduling.

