Anti-viral Therapy in Alzheimer's Disease

NCT03282916

July 14, 2025

Statistical Analysis Plan for "Antiviral therapy: Valacyclovir Treatment of Alzheimer's Disease (VALAD) Clinical Trial"

1. Introduction.

The aim of the study was to evaluate the efficacy of Valacyclovir treatment in a 78-weeks, multicenter, randomized, double-blind, placebo-controlled, parallel-group treatment trial in participants with early Alzheimer's Disease (AD) and positive serum antibodies (IgG or IgM) to HSV1 or HSV2.

This statistical analysis plan provides more detailed descriptions of the statistical analyses conducted in the paper.

2. Study Design

One hundred and twenty participants with clinical diagnosis of probable AD or mild cognitive impairment (MCI), confirmed by a positive amyloid PET or FDG PET scan or a CSF AD profile, were randomized to Valacyclovir or placebo at 1:1 ratio. Block randomization with varying block sizes (2 and 4) was used to reduce the risk of treatment allocation prediction by clinicians. Participants were evaluated at five scheduled visits (weeks 0, 12, 26, 52, and 78). As a proof-of-concept study, the target dose of Valacyclovir was 4 g per day -- at the higher end of the usual oral dosing range. Treatment began at 2 g per day (1 g twice daily), with the dose increased by 1 g per day every two weeks until reaching either 4 g per day or the participant's maximum tolerated dose.

3. Outcome Measures.

1) Cognitive and functional measures:

- Alzheimer's Disease Assessment Scale Cognitive Subscale 11 (ADAS-Cog 11), assessed at weeks 0, 12, 26, 52, 78; scoring range 0-70, higher scores indicate greater cognitive impairment. (Primary)
- Alzheimer's Disease Cooperative Study-Activities of Daily Living Scale (ADCS-ADL), assessed at weeks 0, 12, 26, 52, 78; scoring range 0-78, higher scores indicate better daily functioning. (Secondary)
- Craft story delayed verbatim recall, assessed at weeks 0, 52, 78; scoring range 0-44, higher scores indicating better memory. (Secondary)
- Montreal Cognitive Assessment (MoCA), assessed at weeks 0, 52, 78; scoring range 0 to 30, higher scores indicating better global cognition. (Secondary)

For all cognitive and functional measures, the outcome of interest is the change from baseline at each follow-up time point. The primary endpoint is the change from baseline to 78 weeks.

2) Imaging measures:

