To assess safety, adverse events were systematically evaluated. For each type of adverse event, number and proportion of participants who experienced the adverse event was reported and compared by treatment arms using Fisher's exact test. In addition, plasma acyclovir and CSF acyclovir concentrations obtained at 12 weeks and 78 weeks were summarized using means and standard deviations.

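### The SAP compares adverse events only type by type; adding a comparison of participants with any serious adverse event, with a confidence interval, would be a cheap improvement

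*SAP*

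**What the plan says.** The whole between-arm safety analysis is one sentence in SAP section 5: "For each type of adverse event, number and proportion of participants who experienced the adverse event was reported and compared by treatment arms". The test it names is Fisher's exact test. The protocol's Statistical Analysis Plan section carries the same text. The SAP does not define an event type, does not mention seriousness, and names no summary across types.

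The significance level is 5%, and "There was no adjustment for multiple statistical comparisons in this trial". Participants "were randomized to Valacyclovir or placebo at 1:1 ratio", and the protocol Introduction gives the arm sizes: "The targeted number of participants was reduced from 130 to 120 (60 valacyclovir, 60 placebo").

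The data for a summary across types are largely collected. The protocol section on adverse events defines an SAE to cover medically serious events, any hospitalization and death, whatever the type, and adds: "SAEs are also logged on the AE form for data purposes in this study". The section on early discontinuation lists side effects as a reason for stopping, and the section on dropouts says that the reason for early exit is documented.

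The protocol Background also gives serious harm as a total over types: "valacyclovir 8 g/day was associated with serious adverse events in 10% of patients including GI disturbances and headache, and thrombotic microangiopathy in a few cases". That sentence concerns patients with HIV infection and clinical AIDS.

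**The concern.** Seriousness cuts across event types. If each type is tested separately and seriousness is not used, a serious excess on valacyclovir is divided over several rows, each with few events. Within a row, serious events are also mixed with mild events of the same kind. The result could be a table of non-significant rows that a reader takes as no safety difference. That reading would be weakly founded for a 78-week trial at 4 g/day in older patients, when the data for a more informative comparison are already on file.

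**Working it through.** The documents give no power, event count or detectable difference for safety, so there is no planned figure to reproduce.

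**Inputs.** From the documents: 60 per arm, Fisher's exact test, 5% level, no multiplicity adjustment. Assumed, because the documents do not say: two-sided testing, all 60 per arm evaluable, the placebo SAE rate (0% to 20% shown), a 10-point excess on valacyclovir, and an equal split over three independent types, with each participant's SAE falling in one type.

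**1. Smallest significant row.** With k events v 0 at 60 per arm, two-sided p = 2 × C(60,k)/C(120,k).
- k = 4: p = 0.119
- k = 5: p = 0.057
- k = 6: p = 0.027

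So a type seen in fewer than 6 of 60 participants (10%) in one arm cannot reach 5%, even with none in the other arm. With 1, 2 or 3 events on placebo, the smallest significant counts on valacyclovir are 8, 10 and 11.

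**2. One pooled any-SAE test against three rows.** Exact power is the sum, over all pairs (a, b) with a > b and Fisher p ≤ 0.05, of Bin(a; 60, pV) × Bin(b; 60, pP). For three equal types, both rates are divided by 3 to give the power f of one row. The chance of at least one significant row is 1 − (1 − f)³.

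Worked case, 10% v 0%: pooled power is P(X ≥ 6) for X ~ Bin(60, 0.10) = 0.563. One row is P(X ≥ 6) for X ~ Bin(60, 0.0333) = 0.0148, and 1 − (1 − 0.0148)³ = 0.044.

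| SAE rate, valacyclovir v placebo | Pooled power | Rates in one of 3 types | Power of one row | Any of 3 rows |
|---|---|---|---|---|
| 10% v 0% | 56% | 3.3% v 0% | 0.0148 | 4% |
| 15% v 5% | 33% | 5.0% v 1.7% | 0.0325 | 9% |
| 20% v 10% | 25% | 6.7% v 3.3% | 0.0416 | 12% |
| 30% v 20% | 18% | 10.0% v 6.7% | 0.0447 | 13% |

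The pooled test is ahead in every line, but its lead falls from 52 points to 5 as the placebo rate rises.

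**3. Sensitivity to the split.** For 10% v 0% divided 70/20/10 instead of equally, the rows are 7%, 2% and 1%. Their powers are 0.242, 0.0013 and below 0.0001, so the chance of a significant row is 24%, against 4% under an equal split.

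**4. What an interval adds.** Take 9 of 60 v 3 of 60 participants with an SAE as an example. Fisher p = 0.13 and the risk difference is 15% − 5% = 10 points. The Wilson intervals are 8.1% to 26.1% and 1.7% to 13.7%. Newcombe's limits are:
- lower: 0.10 − √[(0.150 − 0.081)² + (0.137 − 0.050)²] = −0.01
- upper: 0.10 + √[(0.261 − 0.150)² + (0.050 − 0.017)²] = 0.22

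An interval from −1 to +22 points shows that a substantial excess is not excluded. A list of non-significant rows would not show this.

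**The case against.** **A reader might infer that serious harm cannot show up under this plan.** The documents do not support that. Counts and proportions are reported for every type, so an imbalance is visible whatever its p-value. SAE reports go to the DSMB as they arise, and the DSMB receives an unblinded report by arm. That is monitoring during the trial and does not specify the final comparison, but the harm is not hidden.

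**A reader might also take the 10% SAE figure as the rate to expect here.** It comes from patients with HIV infection and clinical AIDS at 8 g/day, twice this trial's target, and it is not a planning rate. It shows only that the protocol itself totals serious harm across types.

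**The contrast in power depends on the assumptions.** This stands. A placebo SAE rate of zero is implausible when any hospitalization counts, so 56% v 4% is the extreme case. The protocol gives no breakdown by type. The split figures also count serious events only, whereas the planned rows include mild events. If a type is common at all grades, its row can be sensitive: an assumed 35% v 10% has 89% power.

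**The main limit is sample size.** This stands too. By the normal approximation, 80% power for a pooled test needs 74 per arm for 10% v 0%, 141 for 15% v 5% and 199 for 20% v 10%. A non-significant any-SAE test could be misread as easily as a list of non-significant rows.

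**Because type is undefined, a row for serious events may have been intended.** The text does not say so, and adding the row settles it.

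**Conclusion.** The point holds as a cheap improvement to the safety analysis. The plan specifies no comparison of participants with any SAE, or of those stopping drug for an adverse event, and its type-by-type tests have little chance of detecting a serious excess spread over several types. For an assumed 10-point excess, pooling raises the chance of a significant result from between 4% and 13% (three equal, independent types) to between 18% and 56%. The gain is smallest at the higher background rates, and it also shrinks with an unequal split. It rests on the assumed rates, the split and two-sided testing at 60 evaluable per arm. The efficacy analysis is not affected.

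**What to change.** Add to SAP section 5 the number and proportion of participants with at least one SAE, by arm, with the risk difference and a 95% CI alongside Fisher's test. Add the same for participants who stopped study drug because of an adverse event. Include dose reduction for an adverse event only if it is recorded; the documents do not show that the adverse event log or exit form captures it. Keep the per-type table and say what counts as a type.

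The SAP is written in the past tense about analyses already conducted, so these rows should be labelled as added to the current plan and not presented as prespecified.

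The cost is a few lines of text and two table rows, mostly from data already held. The downside is two more unadjusted comparisons. Because the pooled test is still underpowered, the text should base its safety conclusion on the confidence interval and not on whether p falls below 0.05.
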